## 7.9 Concomitant medication

All ocular concomitant treatments will be described in each treatment group by defined therapeutic classes (third ATC level: S01A, S01B, S01C, S01E, S01F, S01G, S01H, S01J, S01K, S01L, S01X). The same descriptive analysis will be performed for non-ocular concomitant treatments (first ATC level: A, B, C, D, G, H, J, L, M, N, P, R, V).

All concomitant treatments will also be listed by group.

## 7.10 Compliance and exposure to treatment

Results of statistical tests will be two-sided and given for information purpose only.

Listings of subjects compliance masked data will be provided for the masked review meeting to determine treatment compliance deviations.

### 7.10.1 ART exposure and compliance during screening period

Summary statistics for ART exposure analyses will be presented on the Safety population. ART exposure will also be compared between treatment groups (Student t-test for independent samples or a Wilcoxon rank-sum test if the data do not follow a normal distribution).

ART compliance will include the average daily ART administration and the % of days with at least one instillation. Summary statistics for these data will be provided on subjects of the ITT and PP populations with an evaluable Diary A. Both data will also be compared between treatment groups in the PP population (Student t-test for independent samples or a Wilcoxon rank-sum test if the data do not follow a normal distribution on the average daily ART administration and % of days with at least one instillation).

The ART compliance evaluated by the investigator will also be described in both populations ITT and PP and be compared between treatment groups in the PP population (chi-square test or a Fisher exact test depending on the sample size).

### 7.10.2 Exposure and compliance during treatment period

The exposure to treatment will be described on the Safety population and compared between treatment groups (Student t-test for independent samples or a Wilcoxon rank-sum test if the data do not follow a normal distribution).

Treatment compliance will include the average daily treatment administration, the number and % (compliance rate) of days with 3-6 treatment administrations at D28 and D90. These will be computed on subjects from the ITT and PP populations with evaluable Diaries B and C. Evaluable diary will be defined as Diary with at least 3/4 treatment days filled by the patient. Treatment compliance data will be described at D28 and D90 in ITT and PP populations and compared between treatment groups at D28 on the PP population only (Student t-test for independent samples or a Wilcoxon rank-sum test if the data do not follow a normal distribution on the average daily treatment administration, the number and % of days with 3-6 treatment administrations at D28 and D90).

Subjects will be classified into 3 categories of compliance rate as follows:

1. Between  $\geq 80\%$  and 100% of compliance rate,
2. Between  $\geq 60\%$  and  $< 80\%$  of compliance rate,
3.  $< 60\%$  of compliance rate.

This variable will be described and compared by treatment groups (chi-square test or a Fisher exact test depending on the sample size).

The compliance evaluated by the investigator will also be described at each visit and compared by treatment groups (chi-square test or a Fisher exact test depending on the sample size).

All compliance analyses will be performed on the ITT and PP populations.

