2.2.3 Subject Discontinuation

A subject MAY be discontinued (at the discretion of the Investigator, the Sponsor, and/or the EC) prior to the final visit for several reasons, including, but not limited to:

- A serious adverse event (SAE) occurring during the course of the study, which precludes continued treatment or follow-up
- The subject not following required study procedures
- If a subject exhibits intolerable AEs (related or not related to the investigational medical device), or if a subject fails to show improvement or the clinical status worsens, the treating Investigator may opt to withdraw the subject from the study and implement necessary intervention.

A subject MUST be discontinued prior to the final visit for any of the following reasons:

- Voluntary withdrawal
- Death
- Investigator decision that it is not in the best medical interest of the subject to continue participation in the investigation. In case a subject administers more than 8 instillations per day for both eyes on a regularly continued basis (approximately 70 %) as assessed on Visit 4, the subject will be discontinued from the study and the investigator will prescribe an appropriate treatment.

Prior to discontinuing a subject, every effort should be made to contact the subject, schedule a final visit, obtain as much follow-up data as possible, and to retrieve all investigational materials. Adverse events will be followed as described in Section 6.5 . Subject withdrawals will be documented clearly on the source document and applicable electronic case report form (eCRF). The assessments scheduled for Visit 5 should be performed at this early termination visit.

Notification of subject discontinuation will be made to the Sponsor Representative and will be clearly documented on the applicable eCRF. Any subject discontinued from the study will not be replaced.

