5.1.2 Visit 2 (Baseline/Randomization, Day 0)

- Collect AEs and changes in concomitant medications
- Collect subject diary (Diary A) and review for compliance
- Collect run-in ART
- Determine if the subject meets Visit 2 dry eye eligibility criteria by performing the following:
 - Symptoms assessment
 - VA measurement
 - Biomicroscopy
 - TFBUT measurement
 - Fluorescein staining
- If the subject meets the dry eye eligibility criteria on Visit 2, proceed as follows:
 - Perform the Schirmer test
 - Have the OSD-QoL® questionnaire completed by the subject
 - Dispense the investigational eye drops from the next sequential kit number to the subject
 - Instruct the subject to instill 1 drop of investigational eye drops in each eye 3 to 6 times per day
 - Provide new subject diary (Diary B) to the subject to record investigational eye drop instillation frequency, investigational eye drop tolerability upon instillation and ease-of-use of the bottle
 - Instruct the subject to bring their diary (Diary B) with them to Visit 4
 - Instruct the subject to put their used and remaining unused bottles in the container (kit box provided at Visit 2) for retrieval at the end of the study

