7.6 Statistical Analysis

7.6.1 Methods of Analysis

Summaries for continuous variables will include the sample size (n), mean, standard deviation (SD), median, minimum, and maximum. Calculations will be based on the number of subjects (or eyes) with non-missing values for the study population being summarized.

Summaries for discrete variables will include frequencies and percentages. Percentages will be based on the number of subjects (eyes) with non-missing values. The denominator for percents will be the number of subjects (eyes) from the study population being analyzed. For each subject, baseline will be defined as the last non-missing measure prior to initiation of investigational treatment and endpoint will be defined as the measure of any follow-up scheduled visit. Change from baseline will be defined as (follow-up measure – baseline measure) and will be calculated if both baseline and follow-up endpoint are not missing.

The study eye will be the eligible eye with the highest total ocular surface fluorescein staining score at baseline or, if both eyes are eligible and have the same score, the study eye will be the right eye.

For each subject, the number of investigational eye drops used per day and for how many days during the course of study will be evaluated. It is expected that most subjects will not perform more than 6 applications per day on a continued regularly basis during the study.

The primary performance endpoint (mean change from baseline in total ocular surface fluorescein staining score) will be analyzed using analysis of covariance (ANCOVA) model. The model will include terms of treatment and baseline ocular surface staining score as covariates. Sensitivity analyses including investigator site as covariate will be performed. A 2-sided 95% confidence interval (CI) based on the ANCOVA model will be computed for the effect difference (CBL-102 Eye Drops *minus* Vismed® Multi). Non-

inferiority will be demonstrated if the upper bound of the 95% CI is less than 2 grades in the PP analysis. Supportive analysis of the primary endpoint will be performed on ITT population. The same ANCOVA model used to analyze the primary endpoint will be employed to analyze secondary continuous performance endpoints. Supportive analyses on secondary performance endpoints will be performed in the ITT and PP populations.

Ocular biomicroscopic assessment will be summarized at each visit using discrete summary statistics and presented by treatment.

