7.6.7 Treatment Compliance

Subject treatment compliance rate will be calculated by dividing the total frequency of drop instillations recorded in the diary for a subject across the entire treatment period by the total number of days times the expected frequency of drop instillations per day and then multiplying by 100. e.g., ([total frequency of drop instillations recorded in the diary across the entire treatment period] / [(the total number of days of exposure) x (the expected frequency of drop instillations per day)]) x 100.

Overall investigational medical device treatment compliance will be summarized using continuous summary statistics and presented by treatment group. Treatment compliance will also be presented using discrete summary statistics in the following categories: (< 80%, 80-120%, and > 120%). Percentages will be calculated out of the number of subjects who returned diaries from that dosing period. The number and percentage of subjects in each compliance rate category will be presented by treatment group.

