## 6.5 Compliance and exposure to treatment

Analyzed parameters	Description	Time of evaluation
Compliance evaluated by the investigator		
Diary returned by the patient	Yes / No	D0 / D28 / D90
After review of the subject's diary, has the patient compliance been good?	Yes / No	D0 (ART) / D7 / D28 / D90
Exposure and compliance to ART		
Exposure to ART	Number of ART days between the first ART instillation (date of the screening visit D-14) and the last ART instillation (as collected at D0 in the eCRF)	Between D-14 and D0
Average daily ART administration	Total number of ART administrations (as specified in the Diary A excluding the day of the visits Screening and D0) / Number of completed days in the Diary A excluding the day of the visits Screening and D0	Between D-14 and D0
% of days with at least one instillation	If the number of filled days $\geq$ 3/4 of the interval between D-14 and D0: 100 x Number of days with at least one ART instillation (Diary A) / Number of filled days in Diary A	Between D-14 and D0
Exposure and compliance to treatment		
Exposure to treatment	Number of treatment days between the first investigational drop instillation (date of baseline D0) and the last investigational drop instillation (as collected at the end of the study in the eCRF)	Between D0 and D90 or end of study
Average daily investigational drop administration	Total number of ART administrations (Diaries B+C excluding the day of the visits D0 and D90 or end of study) / Number of completed days in the Diaries B+C excluding the day of the visits D0 and D90 or end of study	Between D0 and D90 or end of study
Compliance at D28	If the number of filled days $\geq$ 3/4 of the interval between D0 and D28: 100 x Number of days with 3 to 6 treatment administrations (Diary B excluding the day of the visits D0 and D28 or end of study) / Number of filled days in the diary B (excluding the day of the visits D0 and D28 or end of study)	Between D0 and D28 or end of study
Global compliance	If the number of filled days $\geq$ 3/4 of the interval between D0 and D90/End of study: 100 x Number of days with 3 to 6 treatment administrations (Diaries B+C Excluding the day of the visits D0 and D90 or end of study) / Number of filled days in the diary B+C (excluding the day of the visits D0 and D90 or end of study)	Between D0 and D90 or end of study

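### The SAP compliance rate scores days above 6 instillations and days below 3 alike, so over-use is not counted by arm, and the departure from protocol 7.6.7 is not listed

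*SAP*

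**What the plan says.** **Regimen.** Protocol 5.1.2: "Instruct the subject to instill 1 drop of investigational eye drops in each eye 3 to 6 times per day".

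**Protocol analysis.** Section 7.6.1 promises that, for each subject, "the number of investigational eye drops used per day and for how many days during the course of study will be evaluated". Section 7.6.7 divides total recorded instillations by days of exposure times an expected daily frequency, which it does not specify. It adds, in percent and by treatment group: "Treatment compliance will also be presented using discrete summary statistics in the following categories: (< 80%, 80-120%, and > 120".

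**Excess-use rule.** Under protocol 2.2.3, if a subject regularly (about 70%) exceeds 8 instillations a day for both eyes, "as assessed on Visit 4, the subject will be discontinued from the study".

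**SAP analysis.** Section 6.5 redefines compliance as "100 x Number of days with 3 to 6 treatment administrations (Diary B" and so on, divided by the filled diary days. Section 7.10.2 continues: "Treatment compliance will include the average daily treatment administration, the number and % (compliance rate) of days with 3-6 treatment administrations". It then says "Subjects will be classified into 3 categories of compliance rate as follows" and gives the classes 80 to 100%, 60 to under 80%, and under 60%. These summaries are for the ITT and PP populations. SAP section 4, which records modifications from the protocol's statistical section, does not mention the new formula or the new classes.

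**The concern.** A rate that credits only days inside 3 to 6 has no direction. A low value may mean too many drops or too few, and the three SAP classes cannot say which. The protocol planned a class for high use, shown by arm. The SAP has no such class and plans no count of days or subjects above 6 a day.

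This matters because part of the primary objective is to assess safety under use 3 to 6 times a day. Frequency within that range is chosen by the subject, and the design masks the investigator. If one product were used more often than the other, a reader would want to know how much use fell outside the regimen, in which direction and in which arm. Similar compliance percentages in the two arms could describe opposite behaviour.

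Instillation frequency is also a secondary endpoint in SAP 3.4.2, but it is absent from the performance-variable table in SAP 6.2. In practice the compliance section alone carries it.

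**Working it through.** The documents give no expected rate of over-use or under-use, so there is no planned figure to reproduce. The check applies the stated formulas to constructed 30-day diaries.

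**1. SAP rate** = 100 × (days with 3 to 6) / (filled days). **Mean per day** = total instillations / filled days.

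| Diary (30 filled days) | SAP rate | SAP class | Mean per day | Days <3 / 3–6 / >6 |
|---|---|---|---|---|
| A: 9/day × 21, 5/day × 9 | 9/30 = 30% | <60% | (189+45)/30 = 7.8 | 0 / 9 / 21 |
| B: 1/day × 21, 5/day × 9 | 9/30 = 30% | <60% | (21+45)/30 = 2.2 | 21 / 9 / 0 |
| C: 7/day × 30 | 0% | <60% | 7.0 | 0 / 0 / 30 |
| D: 2/day × 30 | 0% | <60% | 2.0 | 30 / 0 / 0 |
| E: 9/day × 15, 1/day × 15 | 0% | <60% | (135+15)/30 = 5.0 | 15 / 0 / 15 |
| F: 9/day × 6, 5/day × 24 | 24/30 = 80% | 80–100% | (54+120)/30 = 5.8 | 0 / 24 / 6 |

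The SAP rate cannot tell A from B or C from D. The mean separates both pairs. It does not expose E, whose mean lies inside the regimen although no day does, or F, which sits in the top class with a fifth of its days above 6. Splitting the days by direction separates all six.

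**2. Subjects who meet the excess-use rule.** If the threshold of 8 is counted on the same scale as the diary frequency, a subject above 8 on about 70% of days has at most about 30% of days inside 3 to 6. That subject always falls under 60%, beside the under-users.

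**3. Can the protocol formula be restored?** Let E be the expected daily frequency. For 3 a day to reach 80%, 3/E ≥ 0.8, so E ≤ 3.75. For 6 a day to stay within 120%, 6/E ≤ 1.2, so E ≥ 5. No E satisfies both. With E = 3, a subject at 4 a day scores 133% and is flagged although within regimen. With E = 6, a constant 7 a day scores 117% and is not flagged, while 3 a day scores 50%. With E = 4.5, 3 a day scores 67% and 6 a day scores 133%, so both ends of the permitted range are misclassified.

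**4. The threshold in protocol 2.2.3.** The text does not say whether the count is per eye or summed over the two eyes. If summed, more than 8 a day means more than 8/2 = 4 per eye, which takes in 5 and 6 per eye and so overlaps the regimen in protocol 5.1.2. The result in step 2 would then not follow.

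**The case against.** The strongest reply is that over-use is not hidden. SAP 7.10.2 describes the mean daily number of instillations by arm in ITT and PP and compares it at D28 in PP. SAP 7.2 supplies the median, minimum and maximum, and the template in 7.13.2.1 adds quartiles. If one arm ran well above 6 a day and the other well below 3, the means would show it, as A and B do. A reader might infer from the compliance classes that such arms could not be told apart. The documents do not support that. What remains is narrower: a mean is not a count of over-use, and opposite deviations can cancel within a subject. SAP 6.5 also defines this mean only from D0 to D90 or end of study, and labels its Diary B and C numerator as ART.

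Other outputs touch the question. Discontinuations and reasons are listed by group (SAP 7.3), deviations include product administration (SAP section 5), and investigator-rated compliance is compared by arm. None is directional. The reason codes in SAP 6.8 do not identify over-use, and the compliance listings for the masked review cannot show a difference between arms.

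A reader might also take over-use to be the only exposure problem that forces discontinuation. It is not. Protocol 5.5 also requires discontinuation when failure to follow instructions endangers the subject or the validity of the study, in either direction. Over-use is the one case with a numeric threshold.

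Losing the class above 120% costs little in itself, since step 3 shows that it did not measure over-use reliably. The SAP's 3-to-6 definition suits the regimen better and should stay. That argues for making it directional and recording the change, not for going back.

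**Conclusion.** The point holds as a reporting gap. The SAP rate pools over-use with under-use. The protocol's by-arm high-use class and its evaluation of the number of days have no equivalent in the SAP, and section 4 does not record the departure. Subjects averaging 7.8 and 2.2 instillations a day can receive the same rate of 30% and the same class, and the planned mean does not reveal mixed use.

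The reach is limited. The diaries are constructed and show what the formulas can do, not what will happen. Protocol 7.6.1 expects that most subjects will not regularly exceed 6 a day. Compliance tests are for information only, and neither the primary model nor the non-inferiority decision uses the compliance classes. The statement that a subject meeting the excess-use rule scores at most about 30% depends on counting the threshold on the diary's own scale, which the protocol leaves open.

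**What to change.** - Keep the 3-to-6 definition and make it directional. By arm, for D0 to D28 and for the whole treatment period, report the number and percentage of filled diary days below 3, within 3 to 6 and above 6 instillations, and the mean across subjects of each percentage. Do this in ITT and PP, and also in the Safety population, where adverse events are counted.
- List the departure from protocol 7.6.7 in SAP section 4, with the reason that no single expected frequency fits a 3-to-6 regimen.
- Reconcile the excess-use wording in protocol 2.2.3 with the per-eye regimen in 5.1.2, stating whether the count is per eye or summed. Then also report by arm the number of subjects meeting that criterion at Visit 4. Until this is settled, the count cannot be defined.
- In SAP 6.5, correct the ART label in the numerator of the mean daily number of investigational drops, and define its D28 version, since 7.10.2 compares it at D28.

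The cost is some SAP wording and one extra descriptive table. The diaries already capture the daily count (protocol Appendix B, section 7), so no new data are needed, and the primary analysis does not change.

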## 7.11 Other analyses

The time intervals between the baseline (D0) and each post-baseline visit, between D0 and the last visit and between D0 and the end of treatment will be calculated and described by groups. The dates of first visit of first subject and last visit of last subject will be provided.

## 7.12 Missing data

For subjects who discontinued the study early, analyses of change from baseline to endpoint for continuous variables will be based on the last non-missing post-baseline data (last observation carried forward data imputation methodology).

For safety data, if the causality assessment of an AE is missing, it will be imputed as “Probably” related to the investigational treatment. Likewise, if the severity is missing, the AE will be assessed as “Severe”.

Regarding diaries, missing data will be discussed during the masked review.

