6.7 Causality assessment

The relationship between the use of the investigational medical device (including the procedure) and the occurrence of each adverse event shall be assessed and categorized as follows:

1) Not related: relationship to the device or procedures can be excluded when:

- the event is not a known side effect of the product category the device belongs to or of similar devices and procedures;
- the event has no temporal relationship with the use of the investigational device or the procedures;
- the event does not follow a known response pattern to the medical device (if the response pattern is previously known) and is biologically implausible;
- the discontinuation of medical device application or the reduction of the level of activation/exposure - when clinically feasible - and reintroduction of its use (or increase of the level of activation/exposure), do not impact on the event;
- the event involves a body-site or an organ not expected to be affected by the device or procedure;
- the event can be attributed to another cause (e.g. an underlying or concurrent illness/ clinical condition, an effect of another device, drug, treatment or other risk factors);
- harms to the subject are not clearly due to use error.

In order to establish the non-relatedness, not all the criteria listed above might be met at the same time, depending on the type of device/procedures and the event.

2) Unlikely: the relationship with the use of the device seems not relevant and/or the event can be reasonably explained by another cause, but additional information may be obtained.

3) Possible: the relationship with the use of the investigational device is weak but cannot be ruled out completely. Alternative causes are also possible (e.g. an underlying or concurrent illness/ clinical condition or/and an effect of another device, drug or treatment). Cases where relatedness cannot be assessed or no information has been obtained should also be classified as possible.

4) Probable: the relationship with the use of the investigational device seems relevant and/or the event cannot reasonably be explained by another cause, but additional information may be obtained.

5) Causal relationship (Certain): the event is associated with the investigational device or with procedures beyond reasonable doubt when:

Study #CBL-2017-01- Protocol

- the event is a known side effect of the product category the device belongs to or of similar devices and procedures;

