- the event has a temporal relationship with investigational device use/application or procedures;
- the event involves a body-site or organ that
 - . the investigational device or procedures are applied to;
 - . the investigational device or procedures have an effect on;
- the event follows a known response pattern to the medical device (if the response pattern is previously known);
- the discontinuation of medical device application (or reduction of the level of activation/exposure) and reintroduction of its use (or increase of the level of activation/exposure), impact on the event (when clinically feasible);
- other possible causes (e.g. an underlying or concurrent illness/ clinical condition or/and an effect of another device, drug or treatment) have been adequately ruled out;
- harm to the subject is due to error in use.

In order to establish the relatedness, not all the criteria listed above might be met at the same time, depending on the type of device/procedures and the event.

Related adverse events (including serious adverse events) are AEs with at least a possible relationship to the investigational medical device or procedure.

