6.8 Reporting Adverse Events and Follow-up

Throughout the course of the study, efforts will be made by the Investigator to remain alert to possible AEs that are either systemic or ocular in nature. The period of observation for collection of AEs extends from the time the subject gives informed consent until the last study visit, Visit 5 (Day 90 ± 10 days). The first concern will be the safety of the subject, and appropriate medical intervention will be made.

The Investigator or designee will elicit reports of AEs from the subject at each study visit and record all AEs. An assessment of each event will be made by the Investigator as to severity and causal relationship to investigational medical device, as well as, start and end dates.

The subject will be instructed to contact the Investigator immediately if any unusual systemic or ocular AEs occur between visits.

Additional assessments/visits may be scheduled, as necessary, to ensure the safety of the subject, during the study period. A subject who discontinues due to an AE should be seen for post-study follow-up visits as necessary.

Non-serious AEs that are ongoing at the study exit visit will be followed by the Investigator up to 30 days after the subject exits the study.

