### 6.3 Safety Variables

Topic	Area	Analyzed parameters	Time of evaluation
Bio-microscopic examination	Each eye	
 
- Eyelid Erythema
 
- Eyelid Swelling
 
- Ocular Discharge
 
- Conjunctival Chemosis
 
- Conjunctival Hyperemia
 
- Corneal Erosion
 
- Corneal Edema
 
- Corneal Infiltrates
 
	D0 / D28 / D90
Visual acuity test	Each eye	
 
- LogMAR = -Log(Visual acuity decimal)
 
	D0 / D28 / D90
Adverse events	All body	
 
- At least one AE during the study
 
- At least one TEAE during the study
 
- At least one ADE during the study
 
- At least one serious AE during the study
 
- At least one serious TEAE during the study
 
- At least one serious ADE during the study
 
- At least one unanticipated serious ADE during the study
 
- At least one anticipated serious ADE during the study
 
	During all study
Adverse events	Ocular	
 
- At least one ocular AE during the study
 
- At least one ocular TEAE during the study
 
- At least one ocular ADE during the study
 
- At least one ocular TEAE related (possible, probable, certain) to the eye drops during the study
 
- At least one ocular TEAE related (possible, probable, certain) to the procedure during the study
 
- At least one serious ocular AE during the study
 
- At least one serious ocular TEAE during the study
 
- At least one serious ocular ADE during the study
 
- At least one unanticipated serious ocular ADE during the study
 
- At least one anticipated serious ocular ADE during the study
 
- Ocular AE description
 
	During all study

Topic	Area	Analyzed parameters	Time of evaluation

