#### Safety parameters definitions

- 1) A TEAE (Treatment-Emergent AE) is defined as an AE that meets either of the following conditions:
  - Begins on or after the first instillation of investigational medical device on D0;
  - Begins before D0 and worsens in severity on or after the first instillation of investigational medical device on D0.
- 2) A DD (Device Deficiency) is an inadequacy of the investigational medical device related to its identity, quality, durability, reliability, safety or performance. This may include malfunctions, use error, or inadequacy in the information supplied by the manufacturer.  
It will be detected by any answer "YES" to the question "Has there been a deficiency of the medical device?".
- 3) An ADE (Adverse Device Effect) is an adverse event related to the use of an investigational medical device.  
It will be detected by any answer "YES" to the question "Has there been a deficiency of the medical device?" followed by an answer "YES" to the question "Has this led to an adverse event?".

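### SAP 7.12 imputes missing AE causality one grade above the protocol's rule, and its unrestricted Severe rule can, under some recording conventions, mask worsening of a run-in event

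*SAP*

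**What the plan says.** SAP 7.12 (Missing data) has two rules for incomplete AE records. On causality: "if the causality assessment of an AE is missing, it will be imputed as “Probably” related to the investigational treatment". On severity: "Likewise, if the severity is missing, the AE will be assessed as" Severe. Neither rule refers to when the event began.

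Protocol 6.7 has a five-level causality scale (not related, unlikely, possible, probable, certain) and its own rule for absent information: "Cases where relatedness cannot be assessed or no information has been obtained should also be classified as possible". It sets the cut-off for relatedness as follows: "Related adverse events (including serious adverse events) are AEs with at least a possible relationship to the investigational medical device or procedure". The SAP 6.3 safety variables use the same cut-off, for example "At least one ocular TEAE related (possible, probable, certain) to the eye drops during the study".

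On timing, Protocol 6.8 states: "The period of observation for collection of AEs extends from the time the subject gives informed consent until the last study visit". AEs from the 14 to 16 days of run-in are therefore in the data. Under the SAP safety definitions, which match Protocol 6.1, an AE is treatment-emergent in either of two cases:
- Condition 1: "Begins on or after the first instillation of investigational medical device on D0".
- Condition 2: "Begins before D0 and worsens in severity on or after the first instillation of investigational medical device on D0".

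**The concern.** There are two separate problems.

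First, the protocol and the SAP put an AE with no causality information in different grades. Two programmers, each following one document, would produce different tables of TEAEs by relationship.

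Second, a worst-case severity is conservative for an event that starts on treatment, but not for the pre-treatment grade of a run-in event. Condition 2 compares a later grade with an earlier one. Raising the earlier grade to Severe makes an increase harder to show, which works against detecting treatment emergence.

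Safety over 90 days is part of the primary objectives, and TEAE occurrence is one of the two listed safety endpoints. A rule that decides whether an event counts as treatment-emergent should therefore be explicit.

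**Working it through.** The plan states no figure on this point. The check compares the texts and then lists the grade patterns.

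**1. Causality.** Take an AE with no causality information.
- Protocol 6.7: Possible.
- SAP 7.12: Probably, read here as the protocol's Probable grade.
- Related under Protocol 6.7 and SAP 6.3 (Possible or higher): yes in both cases.

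The pooled related-TEAE rows are therefore identical. The event moves one grade in the TEAE summary by relationship in Protocol 7.6.1. The adverse device effect rows do not move either, because the SAP safety definitions detect those effects from the device-deficiency questions and not from the causality grade.

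**2. Reach of the rules.** AEs are collected from consent and SAP 7.12 has no onset restriction, so both rules cover run-in events. Read literally, a run-in AE with missing causality becomes Probably related to a product not yet given.

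**3. Severity and condition 2.** Neither document lists the AE severity grades, so the scale is an assumption. Number the grades 1 to k, with Severe = 3. The true worsenings are the pairs with later grade above earlier grade, k(k − 1)/2 in all. With the earlier grade replaced by 3 on the same record, condition 2 needs a later grade above 3. The pairs ending at 3 or below are missed: (1,2), (1,3) and (2,3).

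| Assumed scale | True worsenings | Missed, same record | Missed, new AE record |
|---|---|---|---|
| 3 grades, Severe on top | 3·2/2 = 3 | 3 | 0 |
| 4 grades | 4·3/2 = 6 | 3 | 0 |
| 5 grades | 5·4/2 = 10 | 3 | 0 |

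The last column is zero because a new AE with onset on or after Day 0 meets condition 1, where severity plays no part. These are counts of patterns, not probabilities.

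**4. Size.** 84 subjects randomized 1:1 give 84/2 = 42 per arm. One subject is 1/42 = 2.4 percentage points. The documents give no expected number of affected events.

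**5. Check of the remedy, three-grade scale, same record.** Replace the missing earlier grade by 1 instead of 3. Any later grade of 2 or 3 then counts as worsening.
- True worsenings (1,2), (1,3), (2,3): all 3 are detected.
- Unchanged (1,1), (2,2), (3,3): the last 2 are counted as TEAEs.
- Improved (2,1), (3,1), (3,2): the last 1 is counted as a TEAE.

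Using Severe, none of these nine patterns counts as a TEAE. Using the lowest grade, 6 do: 3 correctly and 3 not.

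**The case against.** A reader might infer that a run-in AE with missing severity can never become a TEAE. The documents do not support that. It requires Severe to be the top grade, a missing pre-Day 0 grade alongside a later grade on the same record, and no new AE entry for the worsening. None of these is stated. If each AE has a single severity field and it is blank, no worsening could be shown without imputation either. In the mirror case, with a mild or moderate pre-Day 0 grade known and the later grade missing, imputing Severe makes the event a TEAE, which is conservative. All of this stands and makes the severity point conditional.

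A reader might also infer that the SAP failed to declare a change. SAP 4 lists modifications from the protocol's statistical section only, whereas the rule on missing causality information is in the adverse-event section. Its absence from SAP 4 is not a failure of that list.

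The causality rule can be defended as a residual rule for a blank field, while Protocol 6.7 instructs the assessor. It errs upward, so it does not favour the product. For a run-in AE that never becomes a TEAE it changes almost nothing: SAP 7.4 describes pre-treatment events by system organ and preferred term only, and the related rows cover TEAEs only. Nor does SAP 7.7.4 repeat the summary by relationship promised in the protocol. These points limit the effect. They do not reconcile the two grades, because the protocol's wording expressly covers cases where no information was obtained.

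Finally, missing fields should be rare. Protocol 6.8 has the investigator assess severity and causality for every event, and Protocol 8.3 requires complete eCRFs with queries. That stands as well.

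**Conclusion.** The point holds in limited form. SAP 7.12 and Protocol 6.7 give different grades to an AE without causality information. The effect is one grade in the TEAE summary by relationship, with no change in the pooled related rows.

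Both SAP rules extend to run-in events. Applying Severe to a missing pre-Day 0 grade can mask worsening under condition 2. If Severe is the top grade and the worsening stays on the same record, every such worsening is masked. If higher grades exist, only worsenings that end at Severe or below are masked. If the worsening is entered as a new AE with onset on or after Day 0, none is.

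The number of affected events is unknown and likely very small. The 2.4 points per subject show scale only and are not an expected loss. The case for a change is that a safety rule conflicts with the protocol, its effect on TEAE status is left open, and the correction is cheap.

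**What to change.** Amend SAP 7.12 as follows.

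- (a) Impute missing causality as Possible, consistent with Protocol 6.7.
- (b) Apply the causality imputation to TEAEs only. Apply the Severe imputation only to AEs with onset on or after the first investigational instillation, or to a missing post-Day 0 grade.
- (c) For an AE that starts before Day 0 with missing pre-Day 0 severity, do not use Severe as the comparison grade for worsening. Use the lowest grade, for TEAE determination only.

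Apply (c) before the causality part of (b), so that TEAE status is settled before causality is imputed.

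The cost is a few sentences in the SAP and a small programming condition. The downside of (c) is that some run-in events that did not worsen may be counted as TEAEs, as step 5 of the check shows. That count is conservative and slightly less favourable.
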